8 ADVERSE EVENT REPORTING

Adverse Event Definition

An adverse event (AE) is any untoward medical occurrence in a subject participating in an investigational study or protocol regardless of causality assessment. An adverse event can be an unfavorable and unintended sign (including an abnormal laboratory finding), symptom, syndrome or disease associated with or occurring during the use of an investigational product whether or not considered related to the investigational product.

These events may be:

- a. Definitely related: clearly associated with study drug/treatment
- b. Probably related: likely associated with study drug/treatment
- c. Possibly related: may be associated with study drug or other treatment
- d. Unlikely to be related, or
- e. Definitely not related to the study drug/treatment

For reporting purposes, an AE should be regarded as definitely or probably related to the regimen if the investigator believes that at least one of following criteria are met:

- a. There is a clinically plausible time sequence between onset of the AE and the administration of the study drug or treatment.
- b. There is a biologically plausible mechanism for the study drug or treatment causing or contributing to the AE.
- c. The AE cannot be attributed solely to concurrent/underlying illness, other drugs, or procedures.
- d. A potential alternative cause does not exist.

Serious Adverse Events (SAE): An adverse drug experience occurring at any dose that results in any of the following outcomes:

- a. Death
- b. A life-threatening adverse drug experience
- c. Inpatient hospitalization or prolongation of existing hospitalization
- d. A persistent or significant disability &/or incapacity
- e. A congenital anomaly or birth defect

Important medical events that may not result in death, be life-threatening, or require hospitalization may be considered a serious adverse drug experience when, based upon appropriate medical judgment, they may jeopardize the patient or subject and may require medical or surgical intervention to prevent one of the outcomes listed in this definition. A serious adverse experience includes any experience that is fatal or immediately life threatening, results in a persistent or significant disability/incapacity, requires or prolongs in-patient hospitalization, or is a congenital anomaly, cancer, or overdose.

Other important medical events that may not result in death, not be life-threatening, or not require hospitalization may be considered a serious adverse experience when, based upon

appropriate medical judgment, the event may jeopardize the subject/patient and may require medical or surgical intervention to prevent one of the outcomes listed previously.

Expected adverse events are those adverse events that are listed in the protocol, the study drug labeling or in the study informed consent document.

Unexpected adverse events are those that:

- a. are not described in the labeling as far as the study drug is concerned.
- b. are not anticipated in the study informed consent. This includes adverse events for which the specificity or severity is not consistent with the description in the informed consent.

Unanticipated problem: Per FDA Procedural Guidance for Clinical Investigators, Sponsors, and IRBs (January 2009), A serious problem that has implications for the conduct of the study (requiring a significant and usually safety-related, change in the protocol such as revising inclusion/exclusion criteria or including a new monitoring requirement, informed consent or investigator's brochure).

Unanticipated problem Reporting: Per 21 CFR 312.66, 312.53 (c)(1)(vii), and 56.108(b)(1), should an Unanticipated problem occur during the investigation, the investigator will promptly report all unanticipated problems involving risks to human subjects or others to IRBMED /FDA.

The severity or grade of an adverse event may be measured using the following definitions:

Mild: Noticeable to the subject, but does not interfere with subject's expected daily activities, usually does not require additional therapy or intervention, dose reduction, or discontinuation of the study.

Moderate: Interferes with the subject's expected daily activities, may require some additional therapy or intervention but does not require discontinuation of the study.

Severe: Extremely limits the subject's daily activities and may require discontinuation of study therapy, and/or additional treatment or intervention to resolve.

Event reporting: The study will comply with the IRB & FDA reporting requirements and guidelines.

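### Section 8 grades an adverse event as definitely or probably related on any one of four criteria, including plausible timing alone, which conflicts with its own five-grade scale

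*Combined protocol and SAP*

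**What the plan says.** Section 8 (Adverse Event Reporting) first lists five grades. The top grade reads "Definitely related: clearly associated with study drug/treatment". The second requires a likely association. The third reads "Possibly related: may be associated with study drug or other treatment". The last two are unlikely and definitely not related.

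The next sentence gives an assignment rule, limited to reporting: the event goes into the top two grades "if the investigator believes that at least one of following criteria are met". Four criteria follow in the section. The first, (a), concerns timing only: "There is a clinically plausible time sequence between onset of the AE and the administration of the study drug or treatment". Criterion (b) asks whether the drug could plausibly have produced or added to the event through some mechanism. Criterion (c) asks whether other illness, medication or procedures fail to explain it fully. Criterion (d) asks whether every other possible cause is absent.

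No section requires a combination of criteria, separates *definitely* from *probably*, or says which criteria lead to the three lower grades.

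**The concern.** The scale and the rule can give different answers for the same event. Take an event with plausible timing and an obvious surgical cause. On the scale it is at most *possibly related*. Under the rule, criterion (a) alone makes it definitely or probably related.

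The design makes this case common. Section 3 starts the single 60-minute infusion at the beginning of surgical closure, so events in the PACU and on the ward follow the start of dosing. Section 6.2.3 continues adverse event monitoring through postoperative days 4-7.

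The protocol's own literature supplies an example. Section 1.4 cites a trial in which PACU nausea was 26% with caffeine and 10% in the comparison group. Under the Section 8 rule, a blinded investigator who found the timing plausible would have to put background nausea in the placebo arm into the same top grades as caffeine-induced nausea. What is at stake is the meaning of the grade, and of any related-event count built on it.

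**Working it through.** The plan gives no figure to reproduce here. The check is a logical one, followed by an illustration on assumed frequencies.

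**Step 1: count the patterns.** Each of (a) to (d) is either met or not met, giving 2 × 2 × 2 × 2 = 16 patterns. Under an any-one rule only the pattern with none met escapes the top two grades, so 16 − 1 = 15 of 16 are forced into them. Criterion (a) is met in 8 of the 16, and each of those 8 is forced up whatever the other criteria say.

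**Step 2: remove impossible patterns.** If no alternative cause exists (d), the event cannot be attributed solely to another cause (c), so (d) implies (c). The 4 patterns with (d) met and (c) not met drop out. That leaves 12, of which 11 are forced into the top two grades. It also means that (d) does nothing under an any-one rule, because (c) has already triggered it.

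**Step 3: look at what is left.** The one remaining pattern has implausible timing, no plausible mechanism, full attribution to something else and an existing alternative cause. That describes an event that is unlikely or definitely not related. *Possibly related* therefore has almost no place, and five grades become roughly two.

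**Step 4: illustrate with event frequencies.** The documents give none, so these are assumptions. Let pa be the share of events with plausible timing, and pb and pc the shares meeting (b) and (c), taken as independent, with (d) contained in (c).

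- Any-one rule: share = 1 − (1 − pa)(1 − pb)(1 − pc)
- (a), (b) and (c) jointly, for contrast only: share = pa × pb × pc

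| pa | pb = pc | Any-one rule | (a), (b) and (c) jointly |
|---|---|---|---|
| 0.5 | 0.1 | 1 − 0.5 × 0.9 × 0.9 = 59.5% | 0.5% |
| 0.5 | 0.3 | 1 − 0.5 × 0.7 × 0.7 = 75.5% | 4.5% |
| 0.7 | 0.1 | 1 − 0.3 × 0.9 × 0.9 = 75.7% | 0.7% |
| 0.7 | 0.3 | 1 − 0.3 × 0.7 × 0.7 = 85.3% | 6.3% |
| 0.9 | 0.1 | 1 − 0.1 × 0.9 × 0.9 = 91.9% | 0.9% |
| 0.9 | 0.3 | 1 − 0.1 × 0.7 × 0.7 = 95.1% | 8.1% |

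The share under the any-one rule can never fall below pa, so timing alone sets the floor.

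**Step 5: see where the grade is used.** It is not an endpoint (Sections 2.2 and 7). Section 9 plans no analysis by relatedness, and no adverse event analysis at all. The stopping reasons in Section 12.4.1 do not refer to it.

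**The case against.** The strongest defence is that the sentence is limited to reporting purposes. It can be read as a deliberately low reporting threshold, separate from the five-grade clinical judgement. That is a legitimate aim, but the text does not separate the two: it tells the investigator to regard the event as definitely or probably related, in the scale's own terms.

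A second defence is that criterion (a) is a judgement and not a clock. This stands in part. An investigator may find a late event implausible in timing after one 60-minute infusion, and the effect lasting up to six postoperative days in Section 2.1 concerns pain in laboratory work, not adverse events. Once timing is judged plausible, however, the rule leaves no discretion.

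Some stronger readings are tempting, but the documents do not support them:

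- **Nearly every postoperative event will be graded as related.** The documents give no event frequencies. The pattern counts are counts of logical combinations, not of events.
- **A signal such as arrhythmia would be hidden.** It stays visible by event type, and Section 12.4.1 lists an unstable arrhythmia during infusion without reference to the grade. Blinding and the placebo control should spread over-attribution across both arms alike.
- **Reporting to the IRB or FDA would be inflated.** Section 8 ties prompt reporting to unanticipated problems and otherwise defers to outside requirements. No section makes the top two grades a trigger.
- **The safety conclusion would rest on a related-event count.** No section says so. Section 8 defines adverse events regardless of causality, and Section 12.4.1 has the study team review all of them.

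**Conclusion.** The inconsistency is real and nothing elsewhere in the protocol repairs it. As written, the rule forces 15 of 16 criterion patterns (11 of 12 feasible ones) into the top two grades. Many routine postoperative events in both arms could be placed there on timing alone, and a related-event count would then say little about caffeine. How many events this would be is unknown. The illustrative range of about 60% to 95% rests entirely on assumed, independent frequencies.

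The damage is confined to the causality grading. A comparison of all events by arm would be unaffected, although the plan does not currently schedule one. Efficacy results and stopping reasons are also unaffected. This is a low-priority correction, worth making because it is cheap and best done before events are graded.

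**What to change.** In Section 8, replace the any-one wording so that plausible timing alone supports no more than *possibly related*, and state which combinations of criteria support each grade. A known mechanism should not be mandatory for *probably related*. Requiring (a), (b) and (c) together would bar that grade for any event without a recognised mechanism and so exchange over-attribution for under-attribution.

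One workable mapping, offered as an example:

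- *definitely*: (a) and (d);
- *probably*: (a) and (c) without (d), with (b) as supporting evidence only;
- *possibly*: (a) without (c);
- no higher than *possibly*: (b), (c) or (d) met without (a);
- *unlikely* or *definitely not*: none met.

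Of the 12 feasible patterns, 2 would be definite and 2 probable, so 4 would fall in the top two grades instead of 11.

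If a deliberately low reporting threshold is wanted, state it as *possibly related* or higher and leave the grades alone. Add to Section 9 a table of all adverse events by arm, whatever their attribution.

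The cost is a short rewording in Section 8 and one table. The downside is that fewer events carry the definite or probable label. The lower reporting threshold and the all-event table offset that.

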9 DATA ANALYSIS/STATISTICAL METHODS

9.1 Sample Size Determination

Sample size and power analysis is based on opioid consumption data observed in 102 hysterectomy patients treated at the University of Michigan with patient heterogeneity with respect to CNS involvement in the pain processing summarized by the Fibromialgia Survey score (FM). Acute opioid responses on POD1 varied between 0.7 and 6.5 (mean OME) with the standard deviation varying 3-18, dependent on the tertile of the FM score. Based on these data we hypothesize that caffeine affecting the pain processing system can show a difference as large as 0.7 vs. 6.5 with standard deviations of 3 and 10, respectively. This will give us the power of 83%, with a sample size of 60, to detect the difference by a two-sided ttest with unequal variances. We note that the opioid consumption distribution is of exponential type and therefore sample means, while approximately normal are a rather crude summary of the difference in the OME distribution by group. We therefore consider the above calculation conservative. The expected reserves of power attained through the use of the appropriate longitudinal model (see Analysis of Primary Endpoint) will be used to lend more power to secondary regression and causal analyses involving explanatory variables and potential mediators. We expect a ~10% drop-out rate, and will continue recruitment until the full 71 patients have been recruited (after drop-out).

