9.2.3 Analysis of Primary Endpoint

A generalized linear mixed model will be the primary analytic tool with appropriate datadriven choice of the link function. Linear regression will be used for assessing cumulative opioid consumption through postoperative day three. A separate analysis will entail longitudinal modeling with repeated oral morphine equivalent (OME) measurements (i.e., we will analyze multiple points of the OME curve simultaneously). A Gaussian subjectspecific intercept term will be included to model between-subject differences and the associated correlation structure. The Time variable (main effect, baseline, PACU, POD1-3) will be used to model the pattern of the respective outcome variable (response) over time in the placebo group. The Group variable (an indicator of the caffeine group, main effect) is an indicator of whether the subject received the caffeine intervention. The Group by Time interaction term expresses the differences of caffeine vs. placebo as far as the pattern of response over time is concerned. Final results will be assessed based on the best model selected using Likelihood Ratio tests and Akaike Information Criteria (AIC). In addition to the model specified above, a models will be constructed a) containing the above group and time specification with the addition of demographic variables and b) containing (a) with the addition of intraoperative factors.

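### The 83% power in section 9.1 is for a best-case day-1 contrast, so power for the primary endpoint (through day 3) is undocumented; separately, 71 does not follow from 60 with ~10% drop-out

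*Combined protocol and SAP*

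**What the plan says.** Section 9.1 bases the sample size on "opioid consumption data observed in 102 hysterectomy patients" at the same institution. POD1 responses there "varied between 0.7 and 6.5 (mean OME) with the standard deviation varying 3-18, dependent on the tertile of the FM score". From this the plan supposes that caffeine "can show a difference as large as 0.7 vs. 6.5 with standard deviations of 3 and 10, respectively", and concludes: "This will give us the power of 83%, with a sample size of 60", using a two-sided unequal-variance t-test. It calls the calculation conservative because opioid use is skewed. It also expects spare power from a longitudinal model, which "will be used to lend more power to secondary regression and causal analyses". The synopsis repeats the claim as power above 80%, without naming an endpoint, a time point or an effect size.

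The primary endpoint (section 2.2.1) is cumulative opioid consumption through POD3 or discharge, whichever comes first. Eligibility (sections 3 and 4.1.1) covers adult non-cardiac, non-neurologic, non-major-vascular surgery.

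On numbers, Figure 2 allocates 30 patients to each arm. Section 9.1 ends: "We expect a ~10% drop-out rate, and will continue recruitment until the full 71 patients have been recruited (after drop-out").

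**The concern.** A power statement should concern the endpoint, population and contrast that the trial will test. This one differs on each count:

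- **Time point.** It uses POD1; the endpoint accumulates through POD3 or discharge.
- **Population.** It uses one procedure; the trial enrols a mix.
- **Contrast.** It takes a spread between patient subgroups as the effect of a drug, and takes the whole spread. The fibromyalgia score is neither an eligibility criterion (section 4.1) nor a stratification factor (section 3 names age and gender).

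These are the only power figures in the documents, and the synopsis version carries no qualification, so a reader will take them as the power of the primary comparison. On that basis a null result could not be called adequately powered. The enrolment figures also leave it unclear how many patients are to be randomised and how many analysed.

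**Working it through.** **Inputs.** From section 9.1: means 0.7 and 6.5 (difference 5.8), SDs 3 and 10, total N 60, two-sided Welch test, observed SD range 3 to 18, drop-out about 10%, target 71. From Figure 2: 30 per arm. Alpha is not stated; two-sided 0.05 is assumed.

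**1. The plan's own figure.** Standard error = √(3²/30 + 10²/30) = √3.633 = 1.906. Noncentrality = 5.8/1.906 = 3.04, with Satterthwaite df 34.2. Power from the noncentral t distribution is 84.0%, and 82.7% at 29 per arm. The stated 83% therefore reproduces. With 71 patients (35 caffeine, 36 placebo) the same inputs give 90.2%.

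**2. Can it be carried over to the primary endpoint?** That would need a mean and SD for cumulative use through POD3 or discharge in the enrolled population. The documents give neither, so no calculation is possible.

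**3. Sensitivity on the POD1 scale only.** Same method; caffeine-arm SD is 3 throughout.

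| Difference | Larger SD | Power, N = 60 | Power, N = 71 (35/36) |
|---|---|---|---|
| 5.8 (full) | 10 | 84% | 90% |
| 4.35 (three-quarters) | 10 | 60% | 68% |
| 2.9 (half) | 10 | 32% | 37% |
| 5.8 (full) | 18 | 39% | 46% |

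For the last row at N = 60: standard error = √(9/30 + 324/30) = √11.1 = 3.33; noncentrality = 5.8/3.33 = 1.74. These rows show how far the 83% depends on its two favourable inputs. They are not estimates of power at POD3.

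**4. Does the longitudinal model supply the missing power?** Section 9.1 gives no size for the gain and directs it to secondary and causal analyses. The documents also disagree on which analysis is primary. The synopsis says the analysis will be longitudinal, and section 9.2.3 opens by naming a generalized linear mixed model as the main tool. Section 9.2.3 then says "Linear regression will be used for assessing cumulative opioid consumption through postoperative day three", followed by "A separate analysis will entail longitudinal modeling with repeated oral morphine equivalent (OME) measurements".

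**5. Enrolment.**

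- 60 analysable with 10% loss: 60/0.90 = 66.7, so 67.
- 60 analysable with 15% loss: 60/0.85 = 70.6, so 71.
- 71 enrolled and 60 left: 1 − 60/71 = 15.5% loss.
- 71 enrolled with 10% loss: 71 × 0.90 = 63.9, about 64 left.
- 71 remaining after 10% loss: 71/0.90 = 78.9, about 79 enrolled.

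No 10% rule links 60 to 71, and neither 71 enrolled nor 71 completing agrees with 30 + 30 in Figure 2.

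**The case against.** The best defence is that section 9.1 hides nothing. It names the cohort, the POD1 timing and the SD range, and says the difference is an upper limit. The arithmetic is right. The stated objective is Phase II feasibility. The t-test can be read as a floor for a longitudinal primary analysis in which POD1 is one time level. All of this stands, and it softens the consequence. It does not turn a POD1 figure into power for the cumulative endpoint: the longitudinal gain is unquantified, the remark about conservatism concerns the shape of the distribution rather than the choice of inputs, and the synopsis carries none of section 9.1's qualifications. Nor would it be fair to treat linear regression as settled and dismiss the longitudinal model, since the documents point both ways.

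A further caution is fair. Section 9.1 does not label which tertile had which mean or SD. That 0.7 and 6.5 belong to the lowest and highest score tertiles, or that SD 18 goes with the mean of 6.5, is inference. What the text supports is that the plan used the full range of tertile means and an SD below the largest one observed.

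On enrolment, 71 exceeds the 67 needed, and section 9.2.2 anticipates no missing primary-outcome data because inpatient medication records are available. The mismatch is one of consistency, not a shortfall.

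**Conclusion.** The concern holds in this form: 83%, and the synopsis's figure above 80%, are correct for a best-case POD1 contrast in a single-procedure cohort and are not documented power for the primary comparison. On the POD1 scale, halving the difference takes 84% to 32% at N = 60, and using the largest observed SD takes it to 39% (46% at N = 71). Both rest on the assumed alpha of 0.05 and on the plan's SD of 3 in the caffeine arm.

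A reader might infer that the trial is underpowered for its primary endpoint. The documents do not support that: without a POD3 mean or SD, the power could lie on either side of 80%. A reader might also infer that the 83% is miscalculated, or that the 71 weakens the trial. Neither follows: the figure reproduces to within about one point, and 71 less 10% still leaves about 64.

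The point should be fixed, because the figure will be relied on and the correction is cheap.

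**What to change.** In section 9.1 and the synopsis:

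- Restate the power, or the detectable difference at the fixed N, for cumulative use through POD3, using the overall rather than tertile mean and SD of the source patients, if those data are available. Name the analysis and alpha to which the figure applies.
- If they are not available, say that the present figure is a best-case POD1 figure and is not the power for the primary endpoint.
- If the SD of 10 is kept, give the reason for choosing it from 3 to 18.

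In section 9.1 and Figure 2, state one number randomised and one number analysed that agree with each other and with the drop-out rate. The sponsor has to say what 71 meant.

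The cost is wording, plus one re-run if the data on the 102 patients can still be reached, which the documents do not say. No enrolment is added. The downside is that the stated power may look less favourable.

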9.2 Data Analysis

9.2.1 Analysis Populations

All analyses will come from the same surgical population (adults \geq 18 years of age, presenting for major non-cardiac, non-neurologic, non-vascular surgery).

